9.2.2 SAEs (Including Deaths) and Adverse Events Leading to Study Discontinuation

An SAE is defined as any AE that:

- led to death
- led to serious deterioration in the health of the subject, that either resulted in
 - a life-threatening illness or injury; or
 - a permanent impairment of a body structure or a body function; or
 - in-patient hospitalization or prolongation; or
 - medical or surgical intervention to prevent permanent impairment to body structure or a body function; or
- led to fetal distress, fetal death or a congenital abnormality or birth defect.

TESAEs, TESAEs related to study drug, TESAEs related to study procedure, TESAEs related to device, TESAEs leading to study discontinuation, and TESAEs leading to death will be summarized in the overall summary table, and by SOC and PT as follow:

- TESAE by SOC and PT
- TESAEs related to study treatment (JUVÉDERM VOLITE, JUVÉDERM VOLBELLA, JUVÉDERM VOLIFT, JUVÉDERM VOLUMA, JUVÉDERM VOLUX, and BOTOX cosmetic) by SOC and PT
- TESAEs related to study procedure by SOC and PT
- TESAEs related to device by SOC and PT
- TESAEs leading to study discontinuation by SOC and PT

- TESAEs leading to death by SOC and PT

9.2.3 Adverse Events of Special Interest

Not applicable.

9.3 Analysis of Laboratory Data

Not Applicable.

9.4 Analysis of Vital Signs

Not Applicable.

9.5 Injection Site Response

Subjects will maintain a diary record of the presence, location, frequency, severity (mild, moderate, and severe), and duration of any injection site response (ISR) for 30 days after each filler treatment.

At each visit, the duration of each IRS symptom (redness, pain after injection, tenderness to touch, firmness, swelling, lumps/bumps, bruising, itching, discoloration, and other) will be calculated as Last Occurrence Date in eDiary – First Occurrence Date in eDiary + 1. It will be summarized descriptively using number and percentage of subjects with observed symptom, mean, SD, SEM, median, min, and max, and by categories 1-3 days, 4-7 days, 8-14 days, and 15-30 days.

The number and percentage of subjects with any ISR will be summarized by visit, ISR symptom and maximum severity.

A listing of ISRs will be provided for the Safety Population.

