### 10.3 Injection Site Reactions

Injection site reactions following treatment with dermal fillers include redness, pain after injection, tenderness to touch, firmness, swelling, lumps/bumps, bruising, itching, and discoloration. Subjects will maintain a diary record of the presence, location, frequency, severity, and duration of any ISR for 30 days after each filler treatment.

Subjects will indicate the occurrence of an ISR and severity (none, mild, moderate, severe) of the event. NOTE: ISRs that persist longer than 30 days should be recorded and followed to resolution on the AE eCRF. If an ISR is ongoing or appears after the subject's last study visit, it will be followed up by the sponsor Product Surveillance separate from this study protocol.

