9.2.1 Treatment-Emergent Adverse Events by SOC and PT, and/or Severity

The number and percentage of subjects will be summarized by SOC and PT, and by maximum severity, SOC, and PT as follow:

- TEAEs by SOC and PT
- TEAEs by maximum severity, SOC, and PT

- TEAEs related to study treatment (JUVÉDERM VOLITE, JUVÉDERM VOLBELLA, JUVÉDERM VOLIFT, JUVÉDERM VOLUMA, JUVÉDERM VOLUX, and BOTOX cosmetic) by SOC and PT
- TEAEs related to study treatment (JUVÉDERM VOLITE, JUVÉDERM VOLBELLA, JUVÉDERM VOLIFT, JUVÉDERM VOLUMA, JUVÉDERM VOLUX, and BOTOX cosmetic) by maximum severity, SOC, and PT
- TEAEs related to study procedure by SOC and PT
- TEAEs related to study procedure by maximum severity, SOC, and PT
- TEAEs related to device by SOC and PT
- TEAEs related to device by maximum severity, SOC, and PT
- TEAEs leading to study discontinuation by SOC and PT
- TEAEs leading to death by SOC and PT

The TEAE summary tables will be presented with SOC in alphabetical order and in decreasing frequency within each SOC. If more than 1 AE is coded to the same SOC or PT for the same subject, the subject will be counted only once for that SOC or PT using the most severe occurrence for the summarization by severity.

In addition, the duration of TEAEs will be summarized by SOC and PT. The duration of a TEAE will be calculated as (AE End Date – AE Start Date) + 1, and summarized as:

- 1 – 3 Days
- 4 – 7 Days
- 8 – 14 Days
- 15 – 30 Days
- ≥ 30 Days

The duration summary table will be presented with SOC in alphabetical order and in decreasing frequency within each SOC. If more than 1 AE is coded to the same SOC or PT for the same subject, the subject will be counted only once for that SOC or PT under the maximum duration.

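### SAP 9.5 labels the span from first to last eDiary report as ISR duration, so symptom-free days between separate reports are counted as days with the reaction

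*SAP*

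**What the plan says.** Protocol 10.3 sets up the diary: "Subjects will maintain a diary record of the presence, location, frequency, severity, and duration of any ISR for 30 days after each filler treatment". It gives no formula for duration. ISRs that last beyond 30 days go to the adverse event eCRF.

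SAP 9.5 repeats the diary content and then defines the derived variable. The unit is one value per symptom and visit ("At each visit, the duration of each IRS symptom"), and the value is "calculated as Last Occurrence Date in eDiary – First Occurrence Date in eDiary + 1". It is summarized by mean, SD, SEM, median, minimum and maximum, and "by categories 1-3 days, 4-7 days, 8-14 days, and 15-30 days". The section has no definition of an episode, no rule for symptom-free or missed days between two reports, and no split by location. Subject counts by symptom and maximum severity, and a listing, are planned separately.

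Two other sections bear on the point:

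- SAP 3.3 defines the safety endpoint as the number and percentage of subjects with an AE, an ISR or a device deficiency.
- The SAP section on TEAEs by SOC, PT and severity has its own duration rule, for recorded events: "The duration of a TEAE will be calculated as (AE End Date – AE Start Date) + 1". Its top category starts at 30 days.

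**The concern.** A first-to-last span equals the time with the symptom only if the symptom is reported without a gap. Gaps are plausible here. Protocol 5.1 requires at least two Juvéderm products in at least two areas, and Protocol 6.2.3 allows up to five products at a session. The same symptom can therefore appear at one site early and at another site later. Because the value is per symptom and not per site, the two are joined into one long reaction. One isolated late entry has the same effect.

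At stake is how the duration table reads. Its mean and its 15-30 day row would be taken as showing how long reactions persist within the diary period, yet both can be set by the date of one late report.

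**Working it through.** There is no stated figure to reproduce, so the check applies the SAP formula to example diaries.

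**Inputs.** Formula, unit and categories are from SAP 9.5. The 30-day diary is from Protocol 10.3 and SAP 9.5. The share of symptoms that stop and recur is not given, so it is assumed below.

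**Step 1. Single records.** Span = last day − first day + 1. Days reported = number of days with the symptom.

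| Diary days with symptom | Span (SAP rule) | Category | Days reported | Category |
|---|---|---|---|---|
| 1-5 | 5 − 1 + 1 = 5 | 4-7 | 5 | 4-7 |
| 1, 2, 6 | 6 − 1 + 1 = 6 | 4-7 | 3 | 1-3 |
| 1, 2, 10 | 10 − 1 + 1 = 10 | 8-14 | 3 | 1-3 |
| 1, 2, 25 | 25 − 1 + 1 = 25 | 15-30 | 3 | 1-3 |
| 1-3 at one site, 10-11 at another | 11 − 1 + 1 = 11 | 8-14 | 5 | 4-7 |
| 1 and 30 | 30 − 1 + 1 = 30 | 15-30 | 2 | 1-3 |

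The first row shows that the rule is right for a continuous reaction. The span can never be smaller than the days reported, so the difference has one sign.

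**Step 2. A 2-day reaction with one later report.** Take days 1-2 plus one report on day r, with r from 4 to 30. The span is r and the days reported are always 3. All 27 positions leave the 1-3 day category: r = 4 to 7 (4 positions) goes to 4-7, r = 8 to 14 (7 positions) to 8-14, and r = 15 to 30 (16 positions) to 15-30.

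**Step 3. Effect on the mean, by assumed recurrence share p.** Suppose every reaction lasts 2 days and a share p recurs once, on a day uniform over 4 to 30. The mean of r is (4 + 30)/2 = 17. Mean span = 2(1 − p) + 17p, and mean days reported = 2 + p.

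| p | Mean span | Mean days reported |
|---|---|---|
| 0% | 2.00 | 2.00 |
| 5% | 2.75 | 2.05 |
| 10% | 3.50 | 2.10 |
| 20% | 5.00 | 2.20 |
| 30% | 6.50 | 2.30 |

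**Step 4. Simulated diaries.** These were 200,000 diaries of 30 days per setting. The acute episode starts on day 1 with a geometric length, and isolated reports occur at a fixed daily chance. With mean length 5 days and a 1% chance, the mean span is about 8.1 days against 5.2 days reported. The 15-30 day category holds about 18.6% against 4.5% of records, and 19.5% of records move up at least one category. Over daily chances of 0.5% to 2% and mean lengths of 3 to 7 days, about 9% to 39% move up. At a chance of zero the two measures agree.

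**Step 5. Missed diary entries.** With mean length 5 days, no isolated reports and 10% of entries missed at random, a plain count of reported days averages 4.6, the span 4.9 and the true length 5.0. A plain count therefore has its own downward error. If a missed day between two symptom-positive days is counted as symptomatic, the count equals the span in this setting, because every day inside the span is then either reported or a missed day between positive days.

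**The case against.** The strongest reply concerns importance and remedy, since the arithmetic follows from the formula.

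- **Endpoint.** A reader might infer that a safety endpoint is misreported. SAP 3.3 defines that endpoint as incidence, and the span does not change incidence or maximum severity. This objection stands. The affected output is a descriptive table in a single-arm study, with no test or decision attached.
- **Other information on duration.** A reader might infer that this table is the only account of how long reactions last. It is not: ISRs beyond 30 days go to the AE eCRF and so can reach the TEAE duration summary, and an ISR listing is planned. This also stands. SAP 9.5 remains the only planned summary of duration within the diary period.
- **Size.** A reader might take the simulated figures as the likely inflation. They largely restate the assumed rate. A 1% daily chance over about 25 remaining days puts a stray entry in 1 − 0.99^25 = 22% of diaries by construction, and 2% over 27 days in 1 − 0.98^27 = 42%. Nothing in the documents supports a particular rate.
- **The span is a reasonable convention.** It is explicit, mirrors the TEAE rule and tolerates missed entries. A plain day count treats each missed entry as symptom-free, which understates duration, and the SAP has no rule for missed diary days. This is a good reason to keep the span and not to replace it. It does not justify calling the span a duration. The TEAE parallel is also incomplete, because that rule applies to a recorded event with its own start and end dates.
- **Unseen material.** The programming plan and table specifications are not among the documents and could hold a gap rule. SAP 9.5 refers to neither. The SAP version history says the ISR summaries were revised to suit the data collected, so the eDiary structure needs confirming.

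**Conclusion.** The point holds as a mislabelled measure. SAP 9.5 reports a first-to-last span as duration, and nothing else in the documents corrects it. When a symptom recurs, or appears at two sites at different times within one diary period, symptom-free days are counted and the record can move up one or more categories (days 1, 2 and 25: 3 days reported, tabulated as 25).

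Relative to days reported, the error is only upward, and it is zero for continuous reactions. Its overall size is unknown; the figures in steps 3 and 4 show how it depends on the assumed recurrence rate and do not estimate it for this trial. A reader might also infer that the span joins reactions across treatments. The per-visit wording does not support this, since the natural reading keeps the span within one diary period. ISR incidence, maximum severity and all efficacy analyses are unaffected.

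**What to change.** In SAP 9.5:

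1. Label the present measure 'time from first to last report'.
2. Add the number of diary days on which the symptom is reported, per symptom and visit, with the same statistics and the same 1-3, 4-7, 8-14 and 15-30 day categories.
3. Count a missed diary day as symptomatic if the nearest completed entries before and after it are both symptom-positive, and show the number of missed diary days.

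The added count still pools sites: the two-site example gives 5 days. Its label should say that it covers the symptom at any site. A truly intermittent reaction gets a smaller value on the new row, but the retained span still shows it.

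The cost is one extra set of rows and a small programming change. It needs no new data collection if the eDiary holds dated daily entries, which the sponsor should confirm first.

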### 6.2.2 Visit V1 and V2 (HArmonyCa Lidocaine)

Screening Visit (V0) and first study treatment (V1) may occur on the same day if all screening procedures are completed, results received, and all eligibility criteria (inclusion and exclusion) are confirmed prior to treatment administration. But the subject must be in agreement to do this and must have had sufficient time to understand the study, and the investigator also must judge that the subject had enough time to consider the study. It will be a subject and investigator decision together - in the event of any doubt, the subject should not be treated on the same day.

Subjects who have successfully completed screening (V0) will enter the study at V1. If no HArmonyCa will be administered to the subject, please proceed with study activities for V3 as outlined in Section [6.2.3](#) and [Table 6.1](#).

The following activities will be performed at V1 if HArmonyCa Lidocaine is administered:

- Record concomitant medications.
- Perform urine pregnancy test for women of childbearing potential.
- Record AEs.
- Dispense subject diary to record AEs; counsel subject on diary entries that are needed during the next 30 days.
- Perform facial HArmonyCa Lidocaine injections into areas that the subject desires and qualified for per the inclusion/exclusion criteria and within the approved clinical indications (Section 5.1 and Section 5.2, respectively).

At V2, HArmonyCa Lidocaine touch-up treatment may be performed. If touch-up is not performed, please proceed with study activities for V3 as outlined in Section 6.2.3 and Table 6.1. If touch-up for HArmonyCa Lidocaine is performed, perform the following activities:

- Record concomitant medications.
- Perform urine pregnancy test for women of childbearing potential.
- Record AEs.
- Dispense subject diary to record AEs; counsel subject on diary entries that are needed during the next 30 days.
- Perform facial HArmonyCa Lidocaine touch-up injections into areas that the subject desires and qualified for per the inclusion/exclusion criteria and within the approved clinical indications (Section 5.1 and Section 5.2, respectively).

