2.2 Study Design Overview

This Phase 4 study is a prospective, interventional, multicenter, combination medical device and drug post marketing study. Each subject will be in the study for up to approximately 5 months and act as his/her own control. All products will be used as per their license only. The investigators will perform all treatments and evaluations.

The study is planned to enroll 60 subjects consecutively at approximately 7 study sites in Brazil. Recruitment will also target men, who are typically under-represented in aesthetic studies.

All subjects will sign an informed consent form (ICF) and begin the study at the screening visit (V0). Subjects following screening (V0) will enter the study and receive an initial treatment of HArmonyCa Lidocaine at Visit 1 (V1), followed by Juvéderm fillers at Visit 3 (V3), and BOTOX at Visit 5 (V5) as indicated in the study design diagram ([Figure 1](#)). If the decision is made to not treat with HArmonyCa Lidocaine, the subject may begin with Juvéderm fillers at V1. As indicated in the diagram, touch-ups of HArmonyCa at Visit 2 (V2), Juvéderm at Visit 5 (V5), and BOTOX at Visit 6 (V6) are optional. If a touch-up of HArmonyCa (V2) is not performed, the subject may advance in the study timeline to the next study visit procedures. If a touch-up of BOTOX is not performed, the subject will return on schedule for Visit 7 (V7). A

subject not receiving Juvéderm touch-up would continue with BOTOX treatment (and all study procedures) outlined for V5. To reduce the number of subject visits, V0 can be combined with the initial treatment visit (V1), if judged by the investigator to be appropriate and acceptable for the subject. End of study is the last clinical visit an enrolled subject has in this study, V7 (after approximately 5 months of treatment). Subjects who discontinue prematurely will be asked to return for the last clinical visit for end-of-study data collection. Identical study procedures will not be repeated where the visits are combined. The schedule of activities is shown in [Table 1](#).

Figure 1. Study Design

[figure not shown]

Table 2. Schedule of Activities (SOA)

Study Visit	V0 ¹	V1	V2	V3	V4	V5	V6 ²	V7 ³
Visit window	Screening	Day 1	Day 30	Day 60	Day 90	Day 120	Day 135	Day 150
	(Day -14 to Day -1)	N/A	(30 ± 7 days after V1)	(30 ± 7 days after V2)	(30 ± 7 days after V3)	(30 ± 7 days after V4)	(15 ± 7 days after V5)	(15 ± 7 days after V6)
STUDY TREATMENTS								

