- ¹¹ FACE-Q Scales include Satisfaction with Facial Appearance Scale, Expectations Scale (baseline only), Aging Appraisal, Psychological Function Scale, Social Function Scale, and Satisfaction with Skin Questionnaire.
- ¹² FACE-Q Expectations subscale will not be collected at End of Study.
- ¹³ If HArmonyCa injections are not to be administered to a subject, the subject will begin at Day 1 with V3 study activities (i.e., Juvéderm fillers).
- ¹⁴ HArmonyCa touch-up, if required. If not required, proceed with V3 study activities.

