9.0 Safety Analyses

9.1 General Considerations

- All safety analyses will be conducted by treatment group, gender, and overall, for the Safety Population.

- Adverse events (AEs) will be coded using the medical dictionary for Regulatory Activities (MedDRA). The actual version of the MedDRA coding dictionary will be noted in the statistical outputs and clinical study report.

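### Injection-site reactions are tabulated by visit, but visit number does not fix the filler given, so the V2 result in the HArmonyCA group can pool two fillers

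*SAP*

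**What the plan says.** SAP 9.5 has subjects keep a diary covering, among other features, the "duration of any injection site response (ISR) for 30 days after each filler treatment". The tables built from it are keyed on visit: "The number and percentage of subjects with any ISR will be summarized by visit, ISR symptom and maximum severity". Duration of each symptom is likewise calculated and summarised at each visit. Neither summary names a product or treatment stage, and neither states a denominator. A listing of reactions is also planned.

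SAP 9.1 adds a general rule: "All safety analyses will be conducted by treatment group, gender, and overall, for the Safety Population". SAP 5.0 gives the two treatment groups as HArmonyCA and Non-HArmonyCA.

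The treatment path is flexible. For subjects not given HArmonyCa, the text of SAP 2.2 says: "If the decision is made to not treat with HArmonyCa Lidocaine, the subject may begin with Juvéderm fillers at V1". Footnote 13 of the SAP schedule describes the same path differently: "the subject will begin at Day 1 with V3 study activities". For the optional touch-up at V2, footnote 14 says: "HArmonyCa touch-up, if required. If not required, proceed with V3 study activities". Protocol 6.2.2, in its account of what happens at V2, agrees: "If touch-up is not performed, please proceed with study activities for V3 as outlined in Section 6.2.3 and Table 6.1". In both schedules the V3 activity is Juvéderm injection.

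**The concern.** A table by visit shows reactions by product only if each visit number goes with one filler. Here it may not. Someone in the HArmonyCA group can receive either a HArmonyCa touch-up or a first Juvéderm session at the V2 time point, and both people sit in the same treatment-group column.

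Reactions at the injection site are a named safety endpoint (SAP 3.3) and are solicited after every filler treatment. HArmonyCa is the product that protocol Version 2 was written to add. The product-specific adverse event summaries in SAP 9.2 name the five Juvéderm fillers and BOTOX but not HArmonyCa, which leaves the diary table as one of the few places where a summarised rate for HArmonyCa could appear. A pooled V2 figure would depend on how many subjects had the touch-up as well as on how often each filler causes reactions.

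**Working it through.** The plan gives no figure to reproduce on this point. The check is to trace which filler can fall in each reporting cell, and then to illustrate the size.

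**Step 1: filler by cell.** Inputs: the visit-keyed table (SAP 9.5), the columns (SAP 9.1 and 5.0), and the paths for subjects without HArmonyCa or without its touch-up (SAP 2.2 with footnotes 13 and 14; Protocol 6.2.2). An advanced session could be recorded under its calendar visit number or under the visit whose activities are performed.

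| Cell | Calendar number kept | Recorded as V3 |
|---|---|---|
| V1, HArmonyCA group | HArmonyCa | HArmonyCa |
| V1, Non-HArmonyCA group | Juvéderm | no session |
| V1, overall and gender | can be mixed | HArmonyCa |
| V2, HArmonyCA group | **HArmonyCa touch-up or first Juvéderm** | HArmonyCa touch-up |
| V2, Non-HArmonyCA group | no HArmonyCa | no session |
| V2, overall and gender | can be mixed | HArmonyCa touch-up |

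The treatment-group split separates the fillers at V1 under either rule. It does not do so at V2 in the HArmonyCA group if calendar numbers are kept. Under calendar numbering, V3 could also combine first and second Juvéderm sessions.

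**Step 2: which rule applies.** SAP 2.2 speaks of Juvéderm at V1, which reads as calendar numbering. Footnotes 13 and 14 speak of V3 activities, which can mean either V3 activities carried out at V1 or V2, or a visit recorded as V3. No sentence settles it.

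**Step 3: illustration.** The documents give no reaction rates and no share of subjects with a touch-up, so all of these are assumptions. Let pH = 0.90 be the proportion with a reaction after HArmonyCa, pJ = 0.60 the proportion after Juvéderm, and t the share of the HArmonyCA group that has the touch-up. With calendar numbering:

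V2 rate in the HArmonyCA group = t × pH + (1 − t) × pJ

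- t = 0.75: 0.75 × 0.90 + 0.25 × 0.60 = 0.825
- t = 0.50: 0.50 × 0.90 + 0.50 × 0.60 = 0.750
- t = 0.25: 0.25 × 0.90 + 0.75 × 0.60 = 0.675

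The figure moves from 82.5% to 67.5% while neither filler's own rate changes. Split by filler, V2 would read 90% and 60% throughout. If every subject in the group has the touch-up (t = 1), there is no mixing.

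For V1, with an assumed share h of subjects in the HArmonyCA group, the overall column is h × pH + (1 − h) × pJ. At h = 0.80 this is 0.72 + 0.12 = 0.84, and at h = 0.50 it is 0.45 + 0.30 = 0.75. The group columns beside it still read 90% and 60%.

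**Step 4: denominator.** Footnote 10 of the schedule issues a new diary at a touch-up visit only when an injection took place. If V2 percentages were taken over the whole Safety Population, they would include people with no injection and no new diary at that visit. This arises even when advanced sessions are recorded as V3.

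**The case against.** The strongest reply is that the visits are defined by their treatment. Both schedules place HArmonyCa only at V1 and V2, and Juvéderm only at V3 to V5. Protocol 6.2.2 and 6.2.3 are headed accordingly. Protocol 6.2.3 times V3 from the previous treatment, which suits an advanced session being V3, and footnote 10 ties the V2 diary to a touch-up. On that reading the by-visit table already shows the five stages. This is a fair reading and may be what the database does. It is not stated, however, and the SAP's own text, "the subject may begin with Juvéderm fillers at V1", points the other way. Table specifications sit in a separate document that might settle it, but the SAP does not.

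A second reply is that SAP 9.1 already splits every safety table by treatment group. That is right for V1. A reader might infer from the by-visit layout that V1 reactions cannot be attributed to a filler, and the documents do not support this. The split does not help at V2.

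A third reply is that exposure is summarised by named filler and visit, that exposure and reactions are both listed, and that the study has no aim of comparing reaction rates between fillers. Subject-level attribution does therefore remain possible, and a reader should not infer that the information is lost. A listing is still not a summarised rate.

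Finally, one might infer that a large part of the sample is affected. The documents give no shares, and Protocol 4.4 and SAP 2.3 say that every subject is meant to receive every treatment. That gives no support for assuming that many skip HArmonyCa. It says little about the touch-up, which is optional.

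**Conclusion.** The point holds in a limited form. SAP 9.5 keys the diary reactions on visit, and visit number does not determine the filler. If advanced sessions keep their calendar number, the V2 result in the HArmonyCA group pools HArmonyCa touch-ups with first Juvéderm sessions, and no planned column separates them. The overall and gender columns at V1 and V2 can also be mixed. The V1 treatment-group columns are not.

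The size is unknown. It depends on the recording rule, on touch-up uptake and on how far the two fillers' reaction rates differ, and the documents give none of these. The range of 67.5% to 82.5% rests wholly on assumed inputs. If advanced sessions are recorded as V3, mixing of fillers at V1 and V2 disappears and only the unstated denominator remains. The primary efficacy analysis is not touched. The change is worth making because it gives interpretable rates under either recording rule at little cost.

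**What to change.** In SAP 9.5, replace visit with treatment stage as the row factor for incidence, maximum severity and duration. The stages are HArmonyCa initial, HArmonyCa touch-up, Juvéderm first session, Juvéderm second session and Juvéderm touch-up. Derive the stage from the injection record, not from the visit label, and use the number of subjects injected at that stage as the denominator. Keep the treatment-group, gender and overall columns.

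The cost is one derived variable and revised table headings, since injection and diary data are already collected. The stages still pool the five Juvéderm products, so the table would give rates by stage and not by individual Juvéderm product.

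Stating only the recording rule and the denominator would remove the ambiguity. If the rule turns out to be calendar numbering, though, the V2 result in the HArmonyCA group would stay pooled.
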